6. DOSING DELAYS/DOSE MODIFICATIONS

Subjects will be evaluated for AEs at each visit with the NCI CTCAE v4.0 used as a guide for the grading of severity. Sections below describe safety run-in and stopping rules, dose reduction steps, instructions for initiation of a new cycle of therapy, and dose modifications during a cycle of therapy.

6.1 Safety Run-in and Stopping Rules

Cohort A: ALR cohort

This is an open-label phase 2 study with a safety run-in period. The study can be considered for full enrollment only after the first 6 evaluable subjects have completed the safety run-in period which is defined as 28 days of cycle 1 of treatment, with 2 or less of the 6 evaluable subjects

experiencing potentially drug-related excess toxicities during safety run-in observation. The decision to proceed to full enrollment vs study discontinuation will be made in a Weill Cornell Medicine Data and Safety Monitoring Board (DSMB) Meeting in conjunction with the Investigators after careful consideration of all available safety and laboratory information.

Definition of potentially drug-related excess toxicity during safety run-in phase include:

Hematologic:

- Grade 4 neutropenia (ANC <500/mm³) lasting for >7 days
- Life-threatening Grade ≥ 3 neutropenia (ANC <1,000/mm³) with fever $\geq 38.3^{\circ}\text{C}$
- Grade 4 thrombocytopenia (<25,000/ mm³) that persists for ≥ 7 days
- Grade 3 thrombocytopenia associated with Grade ≥ 2 bleeding or requiring RBC or platelet transfusions

Non-Hematologic:

- Grade 3 tumor lysis syndrome if requiring dialysis
- Grade 3 rash that has not improved within 10 days to at least Grade 1 using a temporary drug hold of all study drugs and administration of up to 100 mg of prednisone PO or equivalent daily
- Grade ≥ 3 nausea, vomiting, or diarrhea uncontrolled by maximal supportive care and persisting greater than 7 days
- Treatment delay of any drug greater than 7 days for toxicity other than rash

In the safety run-in phase, if a subject ends treatment within the first cycle for reasons other than study drug(s) related toxicity (e.g. non-compliant, withdrawal of consent), they will be replaced. In addition, any subject that misses >7 days of acalabrutinib and/or lenalidomide for reasons other than rash will be replaced; subjects with AEs of rash that miss >10 days of acalabrutinib and/or lenalidomide will be replaced unless considered excessive toxicities. Any subject that requires rituximab discontinuation during the first cycle will be replaced.

Trial-wide stopping rule:

In the first 6 patients, if 2 or more experience potentially drug-related excess toxicities during the first cycle as defined in Section 6.1, the study team in conjunction with the DSMB will make a decision as to whether the treatment should be modified or the study halted.

After the first 16 patients, if the proportion of patients with drug-related grade 3 or higher non-hematologic AEs, as defined in Section 6.1, rise above 40% during the first cycle, the study team will temporarily suspend accrual to determine whether modification should be made to the protocol or the study should be halted due to unacceptable toxicity.

Cohort B: ALO feasibility cohort

We plan to expand the study to include a new cohort of 10 MCL patients who will receive treatment with the ALO regimen. The new cohort will contribute to the analysis of safety and feasibility secondary endpoints.

The ALO regimen will be considered feasible if all of the following conditions are met:

- No more than 2 of the 6 first evaluable subjects experiencing potentially drug-related excess toxicities during safety run-in observation, which is defined as 28 days of cycle 1 of treatment.
- No more than 2/10 patients per cohort stop treatment during the first year due to adverse events.

In the first 6 ALO cohort patients, if 2 or more experience potentially drug-related excess toxicities during the first cycle as defined below, the study team in conjunction with the DSMB will make a decision as to whether the treatment should be modified or the study cohort halted.

Definition of potentially drug-related excess toxicity during safety run-in phase include:

Hematologic:

- Grade 4 neutropenia (ANC <500/mm³) lasting for >7 days
- Grade ≥ 3 neutropenia (ANC <1,000/mm³) with fever ≥38.3°C
- Grade 4 thrombocytopenia (<25,000/ mm³) that persists for ≥7 days
- Grade 3 thrombocytopenia associated with Grade ≥2 bleeding or requiring RBC or platelet transfusions

Non-Hematologic:

- Grade 3 tumor lysis syndrome if requiring dialysis
- Grade 3 rash that has not improved within 10 days to at least Grade 1 using a temporary drug hold of all study drugs and administration of up to 100 mg of prednisone PO or equivalent daily
- Grade ≥3 nausea, vomiting, or diarrhea uncontrolled by maximal supportive care and persisting greater than 7 days
- Grade ≥3 LFT elevations that has not improved with maximal supportive care and temporary hold of all study drugs, and persisting greater than 7 days
- Treatment delay of any drug greater than 7 days for toxicity other than rash

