¹⁰ Lenalidomide must be prescribed through and in compliance with the Revlimid REMS® program of Celgene Corporation. Prescriptions must be filled within 7 days. Consideration should be given to prescribing lenalidomide 5 to 7 days in advance of Day 1 of each cycle to allow time for required patient and prescriber surveys, and drug shipment to patient. Any unused Revlimid® (lenalidomide) should be returned to the patient for disposition in accordance with the Revlimid REMS® program.

¹¹ Correlative study blood samples will be collected weekly for cycle 1, on C2D1, C4D1, and C6D1, then following the same frequency as the MRD collection and at time of progression.

¹² Consider weekly CBC for cycle 2 for subjects who have lenalidomide escalated from 15 mg to 20 mg.

¹³ Allow telemedicine / virtual visits after cycle 3 of induction during cycles when there is no infusion treatment, where physical exam, vital signs, height and weight may not be collected.

¹⁴ PT/INR/aPTT, as well as uric acid and phosphate assessments will be collected at baseline, and only if clinically indicated thereafter.

STUDY PROCEDURES – ALO

Table 2. Schedule of ALO Study Procedures¹

Procedure	Screening	Treatment Phase						Therapy Discontinuation	Follow-up Phase
		Cycle 1			Subsequent cycles	Every 3 cycles Year 1	Every 4 cycles Year 2		
		Day 1	Day 8±1	Day 15±1	Day 1±3				
Staging									
Lymph node/tissue biopsy ²	X								
Bone marrow aspirate & biopsy ³	X					Time to confirm CR			
Staging CT scan (or MRI) ⁴	X					X	X	X	X
PET/CT ⁴	X					Time to confirm CR			
MRD Assay ⁵	X					Cycles 6 & 12	X	Every 6cycles	
Laboratory Studies									
CBC with differential	X	X	X	X	X ¹²				X
CMP including LFT	X	X	X	X	X				X
LDH, uric acid ¹⁴ , phosphate ¹⁴ , PT/INR ¹⁴ , aPTT ¹⁴	X	X	X	X	X				X
Creatinine clearance ⁶	X								
Thyroid function test TSH, T4, T3 uptake	X					X	X	X	X
HBsAg, HBsAb, HBcAb, HCV, HIV ⁷	X								
HBV DNA testing ⁷	X					X	X	X	X
Pregnancy testing ⁸	X	X			X				X
Buccal Swab ²	X								
Other Evaluations									
Physical examination / vital signs ¹³	X	X	X	X	X				X
Height & weight	X	X			X				X
ECOG performance status	X	X			X				X
MIPI score	X								
12-lead ECG ⁹	X								
FACT-Lym QOL questionnaires	X					X	X	X	X
Concomitant medications	X	X	X	X	X				X
Register Revlimid REMS® program	X								
Prescribe via Revlimid REMS® ¹⁰		X			X				
Adverse events assessment		X	X	X	X	X	X	X	X
Correlative studies ¹¹		X	X	X	X				X
Obtain Follow-Up treatment									X

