2.2.4 Data with Triple combination

The Nordic lymphoma group reported the triple combination therapy of ibrutinib-lenalidomide-rituximab (ILR) in 50 R/R MCL ¹⁵. During induction, lenalidomide was given 15 mg po daily, days 1-21, ibrutinib 560 mg po days 1-28, rituximab 375 mg/m² iv day 1 in cycle 1, then 1400 mg sc (or 375 mg/m² iv) days 8, 15 and 22 in cycle 1, then day 1 in cycles 3, 5, 7, 9 and 11. During maintenance phase, responding patients continued with ibrutinib 560 mg po days 1-56 and rituximab sc 1400mg day 1 of each cycle until progression. The most common grade 3-4 adverse events were neutropenia (38%), infections (22%), and rash (14%). In evaluable patients, ORR was 83% with CR at 41% and PR at 41%. Median duration of response and PFS has not been reached. Of the 13 patients evaluable for MRD at 6 months, 7/12 patients have achieved molecular remission in blood and 7/13 in bone marrow. Interestingly, the outcomes of patients with mutant TP53 was comparable to patients with wildtype TP53, suggesting that the triple combination might overcome the poor prognosis associated with TP53 mutations.

The ILR triple combination has also been evaluated in frontline FL and R/R DLBCL studies. The Alliance A051103 trial evaluated the combination of lenalidomide, rituximab, and ibrutinib in patients with previously untreated follicular lymphoma ¹⁶. Despite a high response rate, the activity of the regimen was challenged by poor tolerability related primarily to cutaneous toxicity (grade 3 rash at 36%). In R/R DLBCL, the ILR combination of ibrutinib 560 mg once daily, rituximab 375 mg/m² on day one for six cycles and escalating doses of lenalidomide was evaluated in a phase 1b study ¹⁷. Preliminary data showed promising activity for patients with the non-GCB subtype. The most common grade 3-4 adverse events included neutropenia (33%), maculopapular rash (15%), and anemia (11%). Phase 2 portion of the global study is actively accruing at the dose level of lenalidomide 20 mg daily, days 1-21, ibrutinib 560 mg daily, and rituximab monthly x 6.

Taken together, these data suggest activity and feasibility of combining BTK inhibitor with immunomodulatory agent lenalidomide in MCL, but also suggest that a second-generation BTK inhibitor with less cutaneous toxicity, such as acalabrutinib, would be an optimal choice in the front-line setting.

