5.1.1 Induction

Cohort A: ALR cohort

- Cycles 1-12, 1 cycle = 28 days
- Acalabrutinib 100 mg BID continuous
- Lenalidomide on days 1-21 (15 mg for cycle 1, then escalate as tolerated to 20 mg)
- Rituximab 375 mg/m² on days 1, 8, 15, 21 of cycle 1 then day 1 of cycle 4, 6, 8, 10, 12

Cohort B: ALO feasibility cohort

- Cycles 1-12, 1 cycle = 28 days
- Acalabrutinib 100 mg BID continuous
- Lenalidomide on days 1-21 (15 mg for cycle 1, then escalate as tolerated to 20 mg)
- Obinutuzumab on days 1, 8, 15 of cycle 1, day 1 of cycles 2-6, then every 2 cycles

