13. DATA AND SAFETY MONITORING PLAN (DSMP)

This is a multi-institution study. The data and safety monitoring for this study will be overseen by the Weill Cornell IRB as well as the principal investigators from each site. The study will be reviewed by the Weill Cornell Medicine Data and Safety Monitoring Board (DSMB) as an independent means of data and safety monitoring. Enrollment information, adverse event and safety information, protocol changes, and other interim data will be evaluated by the DSMB on an annual basis. After each evaluation, the Board will provide the principal investigator with recommendations for protocol modification, continuation, or termination.

An interim safety analysis will be performed after the first 6 evaluable subjects have completed the safety run-in period which is defined as 28 days of cycle 1 of treatment, to ensure no more than 2 out of the 6 evaluable subjects experiencing potentially drug-related excess toxicities during safety run-in observation (Section 6.1). The decision to proceed to full enrollment vs protocol modification vs study discontinuation will be made in a Weill Cornell Medicine Data and Safety

Monitoring Board (DSMB) Meeting in conjunction with the Investigators after careful consideration of all available safety and laboratory information.

After the first 16 patients, if the proportion of patients with drug-related grade 3 or higher non-hematologic AEs, as defined in Section 6.1, rise above 40% during the first cycle, the study team will temporarily suspend accrual to determine whether modification should be made to the protocol or the study should be halted due to unacceptable toxicity.

Subjects will be followed continuously throughout the study. Subjects may be removed from study treatment as specified in Section 6.6. The cumulative AEs and SAEs will be reviewed by the Sponsor-investigator on an ongoing basis to identify safety concerns. Investigators will discuss with the IRB whether subjects currently receiving therapy may continue as planned, or whether the protocol should be amended to change the study therapy.

We plan to expand the study to include a new cohort of 10 MCL patients who will receive treatment with the ALO regimen. The new cohort will contribute to the analysis of safety and feasibility secondary endpoints.

The ALO regimen will be considered feasible if all of the following conditions are met:

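### In the ALR cohort every numeric cohort-level toxicity rule counts cycle 1 only, so toxicity first seen after the lenalidomide step-up to 20 mg from cycle 2 cannot enter any of them

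*Combined protocol and SAP*

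**What the plan says.** Section 6.1 gives the ALR cohort three numeric rules.

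- **Run-in.** Full enrollment can be considered after six evaluable subjects have "completed the safety run-in period which is defined as 28 days of cycle 1 of treatment", provided two or fewer had excess toxicity. Section 13 repeats this.
- **Trial-wide trigger.** "In the first 6 patients, if 2 or more experience potentially drug-related excess toxicities during the first cycle as defined in Section 6.1", it falls to the study team and the DSMB to decide whether to modify or halt.
- **40% rule.** After 16 patients, should the share with drug-related grade 3 or higher non-hematologic events "rise above 40% during the first cycle, the study team will temporarily suspend accrual". Section 13 carries the same rule, beginning "After the first 16 patients, if the proportion of patients with drug-related grade 3 or higher non-hematologic AEs, as defined in Section 6.1".

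On dose, Section 5.1.1 specifies "Lenalidomide on days 1-21 (15 mg for cycle 1, then escalate as tolerated to 20 mg". Section 5.3.2 starts patients with creatinine clearance of 30 to below 60 ml/min at 5 mg, with a possible rise to 10 mg. It allows an increase only when the preceding cycle needed no modification, interruption or delay for toxicity. Footnote 12 to Tables 1 and 2 adds: "Consider weekly CBC for cycle 2 for subjects who have lenalidomide escalated from 15 mg to 20 mg".

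One numeric rule runs past cycle 1. ALO feasibility (Sections 6.1, 11.1 and 13) also requires that at most 2 of 10 patients come off treatment for adverse events in the first year.

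**The concern.** The run-in is the gate to full enrollment and the 40% rule is the only later numeric brake on ALR accrual. Both close on day 28, and the planned step-up begins with the next cycle. The dose that induction aims for is therefore never observed inside a window that has a number attached.

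The escalation condition sharpens this. Patients who go up to 20 mg are those who got through the preceding cycle without a toxicity-related change, so most of them are not already in the cycle 1 count. A first serious event at 20 mg would occur in just the patients whom the rules have stopped watching.

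At stake is whether an unexpected cluster of toxicity at 20 mg would lead to a pre-planned pause in accrual, or only to one at the discretion of those reviewing the data. Section 2.3 supports the dose by analogy: its mantle cell triplet experience is with lenalidomide 15 mg, and the 20 mg recommendation comes from follicular lymphoma and DLBCL studies. Both use ibrutinib, not acalabrutinib.

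**Working it through.** **Step 1: windows against dose**

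| Rule | Cohort | Window | Can an event at lenalidomide 20 mg count? |
|---|---|---|---|
| Run-in, 2 or fewer of 6 (6.1, 13) | ALR | cycle 1, 28 days | No |
| Trigger, 2 or more of 6 (6.1) | ALR | cycle 1 | No |
| More than 40% after 16 (6.1, 13) | ALR | cycle 1 | No |
| Run-in, no more than 2 of 6 (6.1, 11.1, 13) | ALO | cycle 1, 28 days | No |
| No more than 2 of 10 stopping for adverse events (6.1, 11.1, 13) | ALO | first year | Yes, if it leads to stopping treatment |

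Induction has 12 cycles. One lies inside the ALR rules. The other 12 − 1 = 11, the only induction cycles in which 20 mg is possible, lie outside.

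**Step 2: event counts**

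For 16 patients, 6/16 = 37.5% does not exceed 40% and 7/16 = 43.75% does, so the rule fires at 7 or more. For the run-in, 3 or more of 6 fails the enrollment condition. Exactly 2 of 6 both permits full enrollment and triggers the modify-or-halt decision; those two statements in Section 6.1 need to be reconciled separately. The plan gives no operating characteristics for any of these rules, so there is no stated figure to reproduce.

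**Step 3: size of the blind spot, on assumed rates**

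Let q1 be the chance of a qualifying event in cycle 1, and q2 the chance in cycle 2 among patients without an earlier event. Neither is in the documents. The cumulative rate through cycle 2 is p = 1 − (1 − q1)(1 − q2). For example, 1 − 0.9 × 0.6 = 0.46. The trigger probability is an exact binomial tail, P(X ≥ 7) with n = 16 or P(X ≥ 3) with n = 6, at q1 as written and at p if cycle 2 counted. It assumes one look and one event rate for both rules.

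| q1 | q2 | p | ≥7/16 as written | ≥7/16 through cycle 2 | ≥3/6 as written | ≥3/6 through cycle 2 |
|---|---|---|---|---|---|---|
| 0.10 | 0.20 | 0.28 | 0.0005 | 0.13 | 0.016 | 0.22 |
| 0.10 | 0.40 | 0.46 | 0.0005 | 0.66 | 0.016 | 0.58 |
| 0.20 | 0.20 | 0.36 | 0.027 | 0.34 | 0.099 | 0.37 |
| 0.20 | 0.40 | 0.52 | 0.027 | 0.82 | 0.099 | 0.69 |

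The as-written columns depend on q1 alone. Whatever q2 is, it adds nothing.

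**Step 4: the rule that does reach further**

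For the ALO first-year limit, P(3 or more of 10 stop) is 0.07, 0.32, 0.62 and 0.83 at true first-year stopping rates of 10%, 20%, 30% and 40%. It responds to later toxicity, but only in ALO, only through treatment stops, and with no stated pause in accrual.

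**The case against.** The best defense is that the plan is consistent and not unguarded. The cycle 1 window is stated the same way throughout, and the protocol cites earlier triplet experience at 20 mg. Escalation is conditional for each patient. Sections 6.2 to 6.4 require holds and reductions for toxicity at any dose. The sponsor-investigator reviews cumulative events continuously. The DSMB reviews annually and can recommend modification or termination. The run-in decision itself draws on all safety data then at hand, which may include some cycle 2 data. All of this stands, and it makes the point one of design, not contradiction. None of it sets a cohort-level number, and whether cycle 2 data are seen at the run-in decision is left to chance.

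Four stronger readings are tempting, and the documents do not support them.

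- *That every numeric rule in the trial ends with cycle 1.* The ALO first-year limit does not.
- *That excess toxicity at 20 mg would set nothing in motion.* Individual dose modifications and the reviews above would respond.
- *That the trial could not assess tolerability of the induction regimen.* Tolerability is a secondary objective (Section 1.2), adverse event prevalence over time is exploratory (Section 1.3), and frequencies are tabulated (Section 11.3.3). Stopping rules are not the tolerability analysis.
- *That Section 2.2.4 shows a dose effect on rash*, with 14% at lenalidomide 15 mg in relapsed mantle cell lymphoma against 36% in follicular lymphoma, where 20 mg was the recommended dose. The same section reports 15% in DLBCL under escalating doses, with phase 2 proceeding at 20 mg. The diseases differ, all three regimens used ibrutinib, and Section 6.1 counts a grade 3 rash as excess toxicity only if it fails to improve within 10 days on drug hold and steroids.

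Two further objections limit the remedy. Footnote 12 concerns blood counts and only suggests extra monitoring, while the 40% rule excludes hematologic events; a longer window there would still miss what the footnote watches. And keeping the threshold while lengthening the window raises the chance of suspension at any true rate. Both are fair and are met in the fix.

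**Conclusion.** The point holds for the ALR cohort. All three numeric cohort-level rules count cycle 1 only, lenalidomide is then at most 15 mg, and an event first seen at 20 mg contributes zero to each of them whatever its true rate. That follows from the text alone and needs no assumption.

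Its practical size does rest on assumptions. Over the grid above, the 40% rule fires with probability 0.0005 to 0.027 as written and 0.13 to 0.82 if cycle 2 counted. The grid assumes independent patients, a single look at 16, and the same q2 for all patients without an earlier event, although not all would escalate. The documents supply no rates for this regimen, so the figures show what the rules can and cannot see, not what toxicity to expect.

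This is a gap in pre-specified monitoring that is cheap to close. It is not evidence that 20 mg is unsafe.

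**What to change.** No dose and no patient-level rule needs to change.

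1. In Sections 6.1 and 13, count qualifying events in the 40% rule through the end of cycle 2, the first cycle in which the escalated dose can be given. The text does not fix the cycle of escalation, so say how patients who escalate later are handled.
2. State the chance of suspension under the longer window, and confirm or recalibrate the 40% threshold. With 7 or more of 16, that chance is 0.001, 0.027, 0.175, 0.473, 0.773 and 0.942 at cumulative rates of 10%, 20%, 30%, 40%, 50% and 60%. The team should say which cumulative rate through cycle 2 it regards as acceptable and judge the threshold against it.
3. Schedule a DSMB look at the cycle 2 data of the six run-in patients, including hematologic events, without holding accrual. It would help to report how many of the six started at 5 mg, since they cannot inform on 20 mg.

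The cost is protocol wording and one additional DSMB look; adverse events are already assessed at each visit. The 40% rule would mature 28 days later, and a suspension would become somewhat more likely, by an amount that step 2 makes explicit.

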6.2 Acalabrutinib

Dose modifications for the following treatment-emergent toxicities are provided in Table 4:

- Grade 4 neutropenia (< 500/µL) for > 7 days
- Grade 3 thrombocytopenia in presence of significant bleeding
- Grade 4 thrombocytopenia
- Grade 3 or 4 nausea, vomiting, or diarrhea, if persistent despite optimal antiemetic and/or anti-diarrheal therapy

- Any other Grade 4 toxicity or unmanageable Grade 3 toxicity

Table 4. Drug Modification Actions for Acalabrutinib

Occurrence	Action
1 st – 2 nd	Hold acalabrutinib until recovery to Grade \leq 1 or baseline; may restart at original dose level
3 rd	Hold acalabrutinib until recovery to Grade \leq 1 or baseline; restart at one dose level lower (100 mg QD)
4 th	Discontinue acalabrutinib

If acalabrutinib is reduced for apparent treatment-related toxicity, the dose need not be re-escalated, even if there is minimal or no toxicity with the reduced dose. However, if the subject tolerates a reduced dose of acalabrutinib for \geq 4 weeks then the dose may be increased to the next higher dose level, at the discretion of the investigator. Such re-escalation may be particularly warranted if further evaluation reveals that the AE that led to the dose reduction was not treatment-related. The maximum dose of acalabrutinib is 100 mg BID.

Treatment with acalabrutinib should be withheld for any unmanageable, potentially study drug-related toxicity that is Grade \geq 3 in severity. Acalabrutinib should be discontinued in the event of an acalabrutinib toxicity lasting more than 28 day. Any other clinically important events where dose delays may be considered appropriate must be discussed with the Principal Investigator.

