6.4.3 Skin Rash

For grade 3 maculopapular rash, delay (day 1 of a cycle), or interrupt (days 2 through 28 of a cycle) lenalidomide and acalabrutinib until rash improves to \leq grade 1, then resume with one dose level reduction of lenalidomide and acalabrutinib (Table 7) for the current and all subsequent cycles. Discontinue allopurinol if rash is thought to be at least possibly related to allopurinol.

For any rash with sloughing (Stevens-Johnson syndrome, toxic epidermal necrolysis) or Grade 3-4 bullous dermatitis, discontinue all treatment.

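### ALR run-in: a persistent drug-related Grade 3 rash managed under 6.4.3, with rituximab given on schedule, can miss the literal excess-toxicity definition in 6.1 and be replaced instead of counted

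*Combined protocol and SAP*

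**What the plan says.** Section 6.1 gives Cohort A a run-in of six evaluable subjects over the 28 days of cycle 1. Full enrollment can be considered if at most two of them have a potentially drug-related excess toxicity. A separate trial-wide rule covers the first six patients: two or more such events lead to a decision by the study team with the DSMB.

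Three lines of 6.1 bear on rash:

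- The rash line: "Grade 3 rash that has not improved within 10 days to at least Grade 1 using a temporary drug hold of all study drugs", with daily prednisone capped at 100 mg.
- The delay line: "Treatment delay of any drug greater than 7 days for toxicity other than rash".
- The replacement rule: "subjects with AEs of rash that miss >10 days of acalabrutinib and/or lenalidomide will be replaced unless considered excessive toxicities".

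Rash management is set elsewhere. Section 6.4.3 says: "For grade 3 maculopapular rash, delay (day 1 of a cycle), or interrupt (days 2 through 28 of a cycle) lenalidomide and acalabrutinib", until the rash is Grade 1 or better. It stops all treatment only for sloughing rash or Grade 3-4 bullous dermatitis. Section 6.5 gives reasons to interrupt a rituximab infusion, and rash is not among them. Section 5.4.1.5 permits short steroid courses for rash but does not require them.

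**The concern.** The counting rule presupposes a step that the management rules do not order. A site can comply fully with 6.4.3, give rituximab on its scheduled days, see a Grade 3 rash persist past 10 days, and still not have held every study drug. Read literally, that rash is not on the list. After more than 10 missed days of oral drug, the replacement rule then applies.

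Section 2.2.4 reports 36% Grade 3 rash with the ibrutinib triplet in untreated follicular lymphoma, and gives lower skin toxicity as a reason to prefer acalabrutinib. Rash is therefore a toxicity the run-in should count reliably. With six subjects, one uncounted event is half of the two needed for the review trigger and a third of the three needed to fail the proceed rule.

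**Working it through.** The plan states no operating characteristics for the run-in, so there is no figure to reproduce. The check compares the texts, then the cycle 1 calendar.

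**1. What is held for Grade 3 rash**

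| Place | Lenalidomide | Acalabrutinib | Rituximab |
|---|---|---|---|
| 6.1 rash line (condition for counting) | held | held | held, if a study drug |
| 6.4.3 (management) | held | held | not mentioned |
| 6.5 (rituximab) | – | – | no hold for rash |

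The documents do not define *all study drugs*. Section 6.1 names acalabrutinib and lenalidomide when it means only the oral drugs, which favors reading the wider phrase as including rituximab. If rituximab is not meant, the drug-hold gap closes. The steroid element is a smaller issue, because the line sets a maximum dose and no minimum.

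**2. Other routes to being counted**

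The delay line excludes rash. Section 6.7 requires drug-related rash to settle to Grade 1 before a new cycle, but that governs Day 1 of a cycle, not the later cycle 1 infusions. No other listed line clearly applies.

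**3. Does the case fit inside cycle 1?**

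Inputs: a 28-day run-in (6.1), a 10-day window (6.1), and rituximab on days 8, 15 and 21 after day 1 (5.1.1). Let d be the onset day.

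- Ten days of follow-up need d + 10 ≤ 28, so d = 1 to 18 (18 onset days).
- Rituximab doses due on days d+1 to d+10: two for d = 5–7 and 11–14 (7 days), one for d = 1–4, 8–10 and 15–18 (11 days), none for 0 days. With day 22 (the Table 1 visit) in place of day 21: two for 6 days, one for 12, none for 0.
- Acalabrutinib days missed by day 28, onset-day doses not taken: 29 − d, which exceeds 10 for d ≤ 18 (18 of 18).
- Onset-day doses taken: 28 − d, which exceeds 10 for d ≤ 17 (17 of 18), provided the rash lasts one day longer.

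These counts show that the case is possible on any such onset day. They are not probabilities.

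**4. Which rule is affected, and how**

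- Review trigger: it refers to the first six patients, so a replaced patient is still one of them. The case is missed only because the definition is not met.
- Proceed rule: it refers to six evaluable subjects, so replacement removes the case and brings in another subject.

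**5. Direction only, under assumed rates**

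The documents give no cycle 1 rate of persistent Grade 3 rash with acalabrutinib. Let q be that rate and o the rate of any other excess toxicity, mutually exclusive. If rash is counted, the event rate is o + q. If it is uncounted but the patient stays among the first six, it is o. If every such patient is replaced, the rate among evaluable subjects is o/(1 − q). For example, with o = 10%, P(≥2 of 6) uncounted = 1 − 0.9⁶ − 6 × 0.1 × 0.9⁵ = 11.4%.

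| o | q | ≥2 of first 6: counted / uncounted | ≥3 of 6 evaluable: counted / replaced |
|---|---|---|---|
| 10% | 5% | 22.4% / 11.4% | 4.7% / 1.8% |
| 10% | 14% | 44.2% / 11.4% | 15.4% / 2.4% |
| 20% | 5% | 46.6% / 34.5% | 16.9% / 11.2% |
| 20% | 14% | 66.2% / 34.5% | 33.3% / 14.3% |

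The 14% is the Grade 3–4 rash rate that 2.2.4 reports for the ibrutinib triplet in relapsed disease, regardless of persistence. It serves as a high value, not an estimate. The other rates are arbitrary.

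**The case against.** The strongest reply is that nothing forces the case to be lost. The list of excess toxicities opens with *include*, so it need not be exhaustive. The replacement rule exempts what is *considered* an excess toxicity, which invites judgement about just this patient. Section 6.4.3 does not forbid holding rituximab, and a site might well hold it during a persistent Grade 3 rash. The DSMB decides "after careful consideration of all available safety and laboratory information", and a replaced subject's rash is still on record. Section 2.2.3 says acalabrutinib has not shown ibrutinib's skin toxicity, so such rashes may be few. All of this stands, and it limits the point to a possible undercount. But judgement may differ between sites, and the written definition should not depend on it.

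Replacement also has proper uses. It has no grade limit, and 6.4.3 recognizes rash from another drug: "Discontinue allopurinol if rash is thought to be at least possibly related to allopurinol". The difficulty is only that it does not exclude persistent drug-related Grade 3 rash.

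A later safeguard suspends accrual once 16 patients have been treated. Its condition is "if the proportion of patients with drug-related grade 3 or higher non-hematologic AEs, as defined in Section 6.1, rise above 40" (a percentage, for cycle 1). It is partial, because it comes after the run-in decision and its reference to 6.1 may import the same rash line.

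Three stronger readings are tempting and are not supported:

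- *The plan requires such patients to be replaced.* It does not, for the reasons above.
- *Replacement takes a patient out of the 2-of-6 trigger.* That trigger refers to the first six patients. Replacement acts on the evaluable set of the proceed rule.
- *Table 6 makes holding lenalidomide alone a compliant path.* Section 6.4.3 also holds acalabrutinib, and 6.2 adds: "Treatment with acalabrutinib should be withheld for any unmanageable, potentially study drug-related toxicity that is Grade" 3 or above.

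The rash line names Grade 3 alone, while the gastrointestinal line covers Grade 3 and above. This is minor: 6.4.3 also names Grade 3 for maculopapular rash and handles bullous and sloughing rash separately.

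**Conclusion.** The definition and the management rule do not fit together. In Cohort A, a persistent study-drug-related Grade 3 rash managed under 6.4.3 with rituximab continued can fall outside the literal excess-toxicity list and be replaced. The calendar allows this for every onset day that leaves 10 days of follow-up. The result can be a missed event for the review trigger and a lost subject for the proceed rule.

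The conclusion rests on two assumptions: that *all study drugs* includes rituximab, and that the site gives rituximab as scheduled. The size of the undercount cannot be estimated from the documents. It is possible, not mandated. The point is limited to ALR: the ALO cohort uses the same rash line, but 6.6 can delay obinutuzumab for clinically significant Grade 3 or higher non-hematologic toxicity, and no replacement rule is stated there. The correction should be made because it concerns a stated safety-counting rule and costs almost nothing.

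**What to change.** In 6.1:

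- Count any study-drug-related rash of Grade 3 or higher that is not at Grade 1 or less within 10 days of interrupting lenalidomide and acalabrutinib per 6.4.3, with steroids as clinically appropriate, whether or not the antibody was held.
- State that a subject meeting this criterion is scored and not replaced. Limit rash replacement to rash that does not meet it (lower grade, or not related to study drug).
- Use the same rash line for ALO.

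Table 6 needs no change, since 6.4.3 already adds the acalabrutinib hold.

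The cost is a wording amendment. A few more rash events may count, but the trigger only prompts a decision by the study team and DSMB, not an automatic stop. If the ALR run-in has already been reviewed, its subjects can be checked against the revised line and any rash-related replacement reported.
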